GCP Good Clinical Practice

GDPR General Data Protection Regulation
GMP Good Manufacturing Practice

HRUK Heart Research UK
IB Investigator Brochure
ICF Informed Consent Form

ICH International Conference on Harmonisation of technical

requirements for registration of pharmaceuticals for human

use.

ICU Intensive Care Unit

IMP Investigational Medicinal Product

IMPD Investigational Medicinal Product Dossier

ISF Investigator Site File (This forms part of the TMF)
ISRCTN International Standard Randomised Controlled Trials

Number

LVAD Left Ventricular Assist Device MA Marketing Authorisation

MHRA Medicines and Healthcare products Regulatory Agency

MS Member State

NHSBT NHS Blood and Transplant

NHS R&D National Health Service Research & Development

NIMP Non-Investigational Medicinal Product
NORS National Organ Retrieval Service
PGD Primary Graft Dysfunction
PI Principal Investigator

F-CUSToS Protocol

Version Number 2.0; Dated 30 January 2025

PIC Participant Identification Centre
PIS Participant Information Sheet

PP Potential Participant
QA Quality Assurance
QC Quality Control
QP Qualified Person

RCT Randomised Control Trial REC Research Ethics Committee

RPH Royal Papworth Hospital NHS Foundation Trust

RVAD Right Ventricular Assist Device

SAE Serious Adverse Event SAR Serious Adverse Reaction

SCfCI Sterile Concentrate for Cardioplegia Infusion

SDV Source Data Verification

SNOD Specialist Nurse in Organ Donation SOP Standard Operating Procedure SmPC Summary of Product Characteristics

SSI Site Specific Information

SUSAR Suspected Unexpected Serious Adverse Reaction

TMF Trial Master File

TMG Trial Management Group
TSC Trial Steering Committee
VTE Venous Thromboembolism
WHO World Health Organisation

iii. TRIAL SUMMARY

Trial Title	F easibility study for Randomised Controlled Trial of Cu stodiol-HTK vs S t T homas' solution for cardioplegia and cold static S torage of UK donation after brainstem death hearts in cardiac transplantation.		
Internal ref. no. (or short title)	F-CUSToS		
Clinical Phase	Stage IV		
Trial Design	Single-blind, multi-centre, national, randomised feasibility study.		
Trial Participants	All adult patients undergoing heart transplantation in the UK from a DBD donor.		
Planned Sample Size	50 patients		
Treatment duration	N/A		
Follow up duration	30 days post-transplant implanta	tion	
Planned Trial Period	12 months		
	Objectives	Outcome Measures	
Primary	To assess the feasibility of conducting a randomised controlled efficacy trial comparing Custodiol-HTK and St Thomas' solution for donor cardiac allograft preservation.	Proportion of eligible donor cardiac allografts that are randomised and receive the correct intervention.	
Secondary	To assess clinical outcomes and novel parameters that predict clinically important outcomes.	 Key outcome data completeness Primary Graft Dysfunction rate within 24 hours of transplant implantation. Cardiac Power Output Index at admission to ICU and 6 hours post-operation. Echocardiographic parameters from trans-oesophageal echo immediately after transplant implantation, including: Left Ventricular ejection fraction, left ventricular maximal posterior wall thickness, maximal septal wall thickness, left ventricular function, right ventricular function and the presence/absence of regional wall motion abnormalities 30-day mortality. 6-month survival. 	

	 Development of post-operative complications within 30-days of surgery, including: Dysrhythmias, Myocardial Infarction, Stroke, Acute Graft rejection, Renal Replacement Therapy, Infection (from any
Product(s) Formulation, Dose, Route of Administration i. Custo be per The beheart. HTK ii. St The Infusion SCfC weight 1. D re 2. D So At the	source), Venous thromboembolism, 30-day re- admission, Hyponatraemia (serum sodium <125mEq/L). - Median length of initial ICU stay - Median length of initial in- hospital stay. Solution; St Thomas's solution (Sterile Cardioplegia diol-HTK: at least 3.5L of cold Custodiol-HTK will fused into the aortic root, over at least 10 minutes. ag will be hung at least 60cm above the level of the The heart will then be stored in 2L of cold Custodiol- (2°C – 8°C). omas' solution: Sterile Concentrate for Cardioplegia on (SCfCI) will be diluted by adding 20ml of SCfCI to e of Ringers solution. The volume of reconstituted I perfused into the aortic root will depend on donor at: onor weight 30-70 Kg: administer 1 litre of constituted SCfCI solution onor weight >70 Kg: administer 1.5 L of reconstituted CfCI solution e request of the recipient transplant surgeon, it is
At the permit and/o	CfCI solution
8 C).	

iv. FUNDING AND SUPPORT IN KIND

FUNDER(S)	FINANCIAL AND NON-FINANCIAL
	SUPPORT GIVEN
Heart Research UK	£199,294.37 for consumables.
	Travel expenses for attendance at meetings when
	required (up to £1000)
Pharmapal/[name] Köhler Chemie GMBH	Custodiol-HTK Solution provided free of charge
	for the duration of the study
NHS Blood and Transplant	St Thomas' solution provided as part of the
	National Organ Retrieval Service Protocol

v. ROLE OF TRIAL SPONSOR AND FUNDER

Royal Papworth Hospital NHS Foundation Trust undertakes to adhere to all expectations of a Sponsor as set out by the Health Research Authority Research Governance Framework 2015 and adhere to the Medicines for Human Use (Clinical Trial Regulations) 2004 Act and all applicable amendments. This includes set-up, management, financing, risk assessment, monitoring, audit, statistical oversight, analysis and dissemination of results.

Heart Research UK undertakes to provide funding through reimbursement quarterly to Royal Papworth Hospital NHS Foundation Trust, up to the sum of £199,294.37, over a period of 18 months from the commencement date of the trial.

Heart Research UK has also conducted an independent peer review of the trial by three independent reviewers.

vi. ROLES AND RESPONSIBILITIES OF TRIAL MANAGEMENT COMMITTEES/GROUPS & INDIVIDUALS

The Data Safety and Monitoring Committee (DSMC) will contain an independent chair and an independent statistician and will provide additional independent oversight and assurance of monitoring and safety aspects of the trial. The DSMC will make recommendations to the Trial Steering Committee (TSC) on the management of the trial.

The TSC will be chaired by an independent person and contain at least one layperson. They will meet on a biannual basis and send reports to the sponsor regarding the progress of the trial and adverse events or safety concerns. The TSC will receive recommendations made by the DSMC on the management of the trial and report to the trial management group.

The Trial Management Group will consist of (as a minimum) [name], [name], [name], a designated Clinical Project Manager from Royal Papworth Hospital, and a designated statistician from Royal Papworth Hospital. The TMG will meet on a monthly basis to discuss all aspects of the trial, with a particular focus on recruitment and any adverse events or reactions.

vii. Protocol contributors

[name], Consultant Cardiac and Transplant Surgeon and National Organ Retrieval Service Lead, Royal Papworth Hospital and NHSBT

[name], Professor of Clinical and Experimental Transplantation, University of Cambridge

[name] [name], Clinical Research Fellow, NHSBT

[name], Clinical Trials Unit Operations Manager, Royal Papworth Hospital

1 BACKGROUND

Primary graft dysfunction (PGD) is the leading cause of early mortality after cardiac transplantation, occurring in approximately one-third of cases, with a mortality rate of around 20%(1). PGD was defined, in an ISHLT consensus statement in 2014, as graft failure occurring in the first 24 hours after transplant, not as a result of a discernible cause(2). As a result of this definition, the causes of PGD are complex and difficult to investigate. Lund et al.(3) highlighted the importance of cold ischaemic time as a predictor of mortality, with increasing cold ischaemic time leading to increased short- and long-term mortality. Outcomes significantly deteriorate with a cold ischaemic time greater than 6 hours(4). The principal issues affecting the cold ischaemic heart are the loss of Adenosine Triphosphate (ATP), cellular swelling, extra-cellular oedema, cellular acidosis, calcium overload, endothelial injury and the build-up of oxygen free radicals, which contribute to mitochondrial damage(5). In turn, the release of these toxic metabolites on reperfusion of the heart can cause further injury, termed reperfusion injury. It is the purpose of the cardioplegia/myocardial preservative solution to mitigate these effects and the consensus statement of 2014 specifically highlights "better preservation", including "different additives in solutions", as a prevention strategy for PGD(2).

There are several solutions available and approved for use as myocardial preservatives in cardiac transplantation around the world. In the UK only two solutions are in current use: Sterile Concentrate for Cardioplegia Infusion (Martindale Pharmaceuticals), commonly referred to as St Thomas' Solution, and sometimes marketed as Plegisol; and Custodiol-HTK solution ([name] Köhler Chemie GMBH), sometimes referred to as Bretschneider solution. Currently, St Thomas' solution is used in around 90% of UK heart transplants, primarily because of familiarity and cost, having been developed in the UK and being slightly cheaper than Custodiol-HTK.

St Thomas' solution arrests the heart through its high potassium concentration and the addition of procaine but contains no additives to mitigate the effects of anaerobic metabolism during cold ischaemia(6). Custodiol-HTK contains histidine as a buffer to combat cellular acidosis, mannitol to reduce cellular oedema and α-ketoglutarate and tryptophan to act as free radical scavengers. During routine cardiac surgery, St Thomas' solution must be administered every 20 minutes to maintain cardiac arrest, whilst the cardioplegic effects of Custodiol-HTK have been shown to last for more than 2 hours without reperfusion(7). The national median ischaemic time for Donation after Brainstem Death (DBD) cardiac transplantation is approximately 3 hours – this includes the time from delivery of the myocardial preservative solution to reperfusion of the heart within the recipient(8). During this time no reperfusion of preservative solution can be performed. We, therefore, hypothesise that the use of Custodiol-HTK as cardioplegia and preservative solution for donor hearts will improve outcomes in cardiac transplantation, by providing enhanced cellular protection during cold static storage.

A large retrospective analysis of the American United Network for Organ Sharing (UNOS) database showed that solutions designated by the research team as "cardioplegia solutions", which included St Thomas' and similar solutions, lead to significantly worse outcomes than Custodiol-HTK in heart transplantation(9). Several small animal studies have also suggested improved cardiac preservation with Custodiol-HTK over St Thomas' solution(6, 10-12). A systematic review and meta-analysis of Custodiol-HTK as a cardioplegia solution in cardiac surgery contained a qualitative review of the only 6 human studies investigating Custodiol-HTK in heart transplantation: three case series, two cohort studies and one randomised controlled trial with 48 patients that was insufficiently powered to detect a difference between three solutions (Custodiol-HTK, UW and Celsior)(13). Unfortunately, this merely highlighted the paucity of evidence comparing myocardial preservative solutions in transplantation, with the authors concluding: "The pre-clinical data is sufficient to encourage large-scale, quality randomised trials to answer the compelling question of which preservation solution provides optimal protection for the cardiac allograft."

F-CUSToS Protocol

Version Number 2.0; Dated 30 January 2025

2 AIMS

Custodiol-HTK and St Thomas' solution have never been directly compared in a randomised controlled trial of human cardiac transplantation. The overall aim of this research project is to investigate the two solutions currently in use in the UK, by performing a high-quality, multi-centre, randomised controlled trial comparing St Thomas' solution with Custodiol-HTK for myocardial preservation during cold static storage of cardiac allografts from DBD donors. The solutions will be compared in the post-marketing authority state, delivered in the form and administration route for which they are approved. The primary outcome of interest is PGD, as this is a significant clinical challenge in cardiac transplantation and its incidence is highly likely to be affected by the quality of myocardial preservation during cold static storage, as highlighted by the ISHLT 2014 consensus statement(2). PGD not only results in higher earlier mortality and morbidity but also has significant cost implications for the healthcare provider. For example, patients with PGD have a median length of ICU stay of 14 days, compared to 5 days without PGD(14). Furthermore, patients without PGD have significantly lower use of mechanical circulatory support (MCS), as well as significantly lower use of renal replacement therapy, need for a return to theatre and inotrope use(14). Just one extra night in ICU is thought to cost around £1,600(15), whilst one day of extra-corporeal membrane oxygenation (the main type of MCS used in this setting) costs approximately £6,000-£12,000(16), without factoring in increased staffing and other resource costs. Therefore, if our trial shows a reduction in PGD with one solution, this could have significant cost implications for the NHS.

Despite the potential cost savings and healthcare outcome benefits of any reduction in PGD, detecting a clinically meaningful difference between the two solutions will require a large sample size. Informing this sample size calculation is complex, because of the lack of high-quality data comparing the two solutions. A power calculation for a superiority trial based on the development of primary graft dysfunction as the primary outcome showed that a sample size of 400 patients would allow detection of a 14% absolute risk reduction in PGD between the two solutions of interest (from 36% to 22%) corresponding to an odds ratio of 0.5 (or 17 cases of PGD prevented per year) with a probability (power) of 0.85 with a type I error of 0.05 when considering a two-sided test of difference in proportions. As approximately 120 adult DBD heart transplants are performed in the UK each year, we estimate that the larger trial will take 5 years to complete (i.e., $80 \times 5 = 400$).

Therefore, we intend to perform a feasibility study to see if we can recruit sufficient patients within a reasonable timeframe, in order to justify undertaking such a large national clinical trial.

The research project has been discussed at a focus group with the Royal Papworth Hospital patient representatives [name] and [name]. They felt this to be a very worthwhile study and that the primary outcome is likely to be achievable. The study Protocol was modified based on their feedback.

2.1 Assessment and management of risk

This trial is categorised as Type A (No higher than the risk of standard medical care).

Both St Thomas' solution and Custodiol-HTK hold MHRA approval for use as cardioplegia and preservative solutions during cardiac transplantation in the UK. Both have excellent safety profiles and are routinely used, although St Thomas' solution is used most frequently as it forms part of the UK National Organ Retrieval Service (NORS) Protocol for cardiac allograft retrieval. Therefore, there is

not thought to be any additional risk, beyond the risks associated with undergoing a cardiac transplant, to participants as a result of taking part in this study.

3 OBJECTIVES AND OUTCOME MEASURES/ENDPOINTS

3.1 Primary objective

To assess the feasibility of conducting a national, single-blind, randomised controlled efficacy trial comparing the effect of using Custodiol-HTK or St Thomas' solution as cardioplegia and preservative solution during cardiac transplantation of UK DBD donor hearts on the rate of PGD.

Hypothesis:

It is feasible to conduct the above trial in the UK within 5 years.

3.2 Secondary objectives

Secondary Objective 1:

To compare the effect of Custodiol-HTK solution and St Thomas' solution on the outcomes of cardiac transplantation from donation after brainstem death (DBD) donors.

Hypothesis 1:

There will be a difference between the two solutions in terms of primary graft dysfunction and 30-day mortality.

Secondary Objective 2:

To investigate the effects of Custodiol-HTK solution on the transplanted heart in terms of haemodynamic performance.

Hypothesis 2:

There will be a difference between the two preservation methods in terms of haemodynamic performance, specifically cardiac power output index in the first 6 hours after transplant.

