3.3.3 Exploratory endpoints

Cardiac Power Output Index (CPOi) at admission to ICU post-transplant implantation and at 6h post-operation will be recorded. The difference between CPOi within individuals at admission to ICU and 6h post-operation will be calculated. Cardiac Power Output is defined as the hydraulic energy created by the ventricles per unit time. It is the product of Cardiac Output (CO), measured by Swan Ganz, and the Mean Arterial Pressure (MAP), taking into account the filling state of the individual and indexed to body size. It has been validated as a measure of pump failure in patients with cardiogenic shock. Primary graft dysfunction is effectively the failure of the cardiac allograft to generate sufficient cardiac output and therefore it has been hypothesised that low cardiac power output after transplantation will correspond to the development of PGD and the requirement for mechanical circulatory support. CPOi on admission to ICU has been shown to be correlated with donor to recipient heart mass ratio and inversely correlated to cardiopulmonary bypass time. Previous work from Birmingham has determined a rule-in, rule-out algorithm for cardiac power index as a predictor of severe PGD and early mortality.

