3.3.4 Table of endpoints/outcomes

Objectives	Outco	ome Measures	this (epoint(s) of evaluation of outcome measure (if icable)
Primary Objective:	The proportion of eligible donor		At th	e end of recruitment.
To assess the feasibility of	cardiac allografts that are			
conducting the CUSToS study.	rando	mised and that receive the		
	correct intervention.			
Secondary Objectives:	i.	The proportion of	iiv.,	, viiviii., xxi. At the end
To compare the effect of		eligible recipients who	of rec	cruitment
Custodiol-HTK solution and St		consent to take part in	vvi.	24-hours post-
Thomas' solution on the		the study.	trans	plant
outcomes of cardiac	ii.	The proportion of	ix.	30-days post-transplant
transplantation from donation		eligible donor cardiac		
after brainstem death (DBD)		allografts where		
donors.		randomisation occurs		
		according to the		
		Protocol.		
	iii.	The proportion of		
		eligible donor cardiac		
		allografts where the heart		
		is preserved in the		
		correct randomly		
		allocated solution.		
	iv.	Key outcome		
		completeness		
	v.	The development of		
		PGD, measured at 24-		
		hours post-transplant		
	vi.	Left Ventricular ejection		
		fraction, left ventricular		
		maximal posterior wall		
		thickness, maximal		

		UK
	septal wall thickness, left	
	ventricular function,	
	right ventricular function	
	and the presence/absence	
	of regional wall motion	
	abnormalities measured	
	on trans-oesophageal	
	echo immediately after	
	transplant implantation	
	vii. 30-day all-cause	
	mortality	
	viii. 6-month survival	
	ix. Development of post-	
	operative complications	
	within 30 days of	
	transplant x. Median length of initial	
	ICU stay in hours	
	xi. Median Length of initial	
	hospital stay in days	
Exploratory Objectives:	Cardiac Power Output Index,	At admission to ICU and 6 hours
To assess CPOi as an outcome	absolute differences between the	post admission to ICU
measure for predicting PGD	groups (PGD/No PGD and	
	Custodiol-HTK/St Thomas') and	
	change over time within and	
	between groups	

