- iii. Body surface area calculated using the DuBois and DuBois formula: Body Surface Area= 0.007184 x (Height(m) $^{0.725}$) x (Weight(kg) $^{0.425}$).
- iv. Mean Arterial Pressure (mmHg) on invasive intra-arterial blood-pressure monitoring at the time of Swan-Ganz measurements.
- v. Central Venous Pressure (mmHg) on invasive central venous pressure monitoring at the time of Swan-Ganz measurements.

As this is an exploratory outcome measure, with the intent to assess its utility based on real-world data, this will be assessed based on the above data being recorded on the intensive care electronic health record system. The measurements will be taken and recorded by the healthcare professional(s) looking after the participant. Where the outcome assessor transferring this data from the healthcare record to the trial database cannot find a measurement within the stipulated timeframe, this will be treated as missing data.

PGD will be determined based on the ISHLT consensus statement 2014 (2) and graded accordingly. PGD is defined as occurring within 24 hours, therefore all measurements included below must be taken within the first 24 hours after admission to ICU post-transplant procedure. Its definition requires the following variables to be recorded on the database:

F-CUSToS Protocol

Version Number 2.0; Dated 30 January 2025

- Ejection fraction on echocardiogram; where multiple measurements are taken the lowest estimate of ejection fraction recorded will be inputted to the database.
- ii. Haemodynamic variables taken at the time of a Swan Ganz measurement*:
 - (i) Central Venous Pressure (mmHg)
 - (ii) Pulmonary capillary wedge pressure (mmHg)
 - (iii)Cardiac Output (L/min)
 - (iv) Cardiac Index (L/min/m2)
 - (v) Mean Arterial Pressure (mmHg)
 - (vi)Transpulmonary gradient (mmHg)
 - (vii) Pulmonary artery systolic pressure (mmHg)
- iii. Vasoactive Inotrope Score (VIS), where VIS = dopamine [μ g kg⁻¹ min⁻¹] + dobutamine [μ g kg⁻¹min⁻¹] + 100×adrenaline [μ g kg⁻¹ min⁻¹] + 50×levosimendan [μ g kg⁻¹ min⁻¹] + 10×milrinone [μ g kg⁻¹ min⁻¹] + 10 000×vasopressin [units kg⁻¹ min⁻¹] + 100×noradrenaline dose [μ g kg⁻¹ min⁻¹].
- iv. Presence/absence of an intra-aortic balloon pump (IABP).
- v. Presence/absence of mechanical circulatory support (ECMO/LVAD/RVAD/BiVAD).

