10.3.3 Secondary outcome analysis

Credible intervals for proportions:

(Such as "the proportion of eligible recipients who consent to take part in the study)
95% Jeffreys credible interval with equal-tail probabilities will be defined for the proportions of interest.

Tests of differences in proportions:

(Such as the difference in PGD rates between the two solutions of interest)

Difference between two proportions defined on independent samples will be assessed by means of exact fisher or score tests. 95% CI for the difference in proportions will be defined by inverting the score test. Logistic regressions may be considered to control for selected confounders. Penalised likelihood will be used in case of perfect separation of the binary outcome by a set of predictor levels.

Tests of independence between pairs of categorical variables:

(Such as the association between grade 3 PGD and treatment)

The independence of rows and columns of contingency table with fixed marginals will be assessed by means of Fisher's exact tests. Ordinal regressions may be considered to control for selected confounders. Partial proportional odds models will be considered if the proportional odd assumption is violated.

Test of equality of two independent means for continuous outcomes:

(Such as the equality of means of some echocardiographic parameter per treatment group)

Welch t-tests will be used to compare the means of two independent samples for continuous outcomes. Transformations (like log, box-cox) will be used in case of strong deviations to normality of the residuals within each group. Wilcoxon rank sum tests may be used as sensitivity analyses or when the comparison of medians (instead of means) is preferred. Linear regressions may be considered to control for selected confounders. Generalized Additive Models for Location, Scale and Shape models will be preferred in case of the presence of heteroscedasticity.

Test of equality of two independent means for bounded outcomes like proportions:

(Such as the association between left ventricular ejection fraction and treatment)

Welch t-tests will be used to compare the means of two independent samples for bounded outcomes like proportion. Transformations (like log, box-cox) will be used in case of strong deviations to normality of the residuals within each group. Wilcoxon rank sum tests may be used as sensitivity analyses. Beta regressions may be considered to control for selected confounders.

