10.5 Adjusted analysis

F-CUSToS Protocol Version Number 2.0; Dated 30 January 2025

As outlined above, risk adjustment for baseline value of CPOi (at admission to ICU) will be used in the linear regression for difference in CPOi between admission to ICU and 6 hours post-transplant. All linear and logistic regression models will be adjusted for confounders of interest and presented alongside single comparison tests, such as Fisher's exact test without adjustment.

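### Protocol 3.2 sets between-arm efficacy hypotheses that the protocol's own figures show 50 patients cannot test, leaves the clinical comparisons without an exploratory label, and classifies CPOi inconsistently

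*Protocol*

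**What the plan says.** Section 3.2 attaches a predicted result to each secondary objective. Hypothesis 1 reads "There will be a difference between the two solutions in terms of primary graft dysfunction and 30-day mortality". Hypothesis 2 reads "There will be a difference between the two preservation methods in terms of haemodynamic performance, specifically cardiac power output index in the first 6 hours".

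Section 10.3.3 gives methods by type of outcome. For proportions, "Difference between two proportions defined on independent samples will be assessed by means of exact fisher or score tests", with a 95% interval from inverting the score test. Means get Welch t-tests and survival gets log-rank tests. Section 10.5 adds: "All linear and logistic regression models will be adjusted for confounders of interest and presented alongside single comparison tests". It also describes a regression of the change in CPOi from ICU admission to 6 hours, adjusted for the admission value.

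Section 3.3.2 lists the clinical endpoints as items v to xi: PGD, echocardiography, 30-day mortality, 6-month survival, complications and two lengths of stay. None is labelled descriptive or exploratory.

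CPOi has two statuses. The trial summary lists it among the secondary outcome measures, and 3.2 makes it the named endpoint of a secondary hypothesis. Section 3.3.3 places it under exploratory endpoints ("Cardiac Power Output Index (CPOi) at admission to ICU post-transplant implantation and at 6h post-operation will be recorded"). Section 3.3.4 lists it under exploratory objectives ("To assess CPOi as an outcome"). Section 7.7 says of it: "As this is an exploratory outcome measure, with the intent to assess its utility based on real-world data".

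On size, section 10.1 says a feasibility study needs no formal calculation and gives only the precision of the feasibility proportion with 50 hearts. Sections 2 and 10.2 put the main trial at 400 patients for PGD 36% versus 22%, power 0.85, two-sided 5%.

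**The concern.** A hypothesis stated as a prediction, followed by a named test, invites a verdict of supported or not supported. Sections 2 and 10.2 say in effect that a sample of this size cannot give that verdict for PGD. Two misreadings are then open. The probable one is a non-significant PGD comparison reported as Hypothesis 1 not supported, which would say almost nothing about whether the target effect exists. The other is an isolated nominally significant result among the many listed endpoints, reported as a difference between solutions. Either could colour the case for the main trial, which this study exists to inform.

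The CPOi conflict adds to this. One part of the protocol asks whether CPOi differs between solutions as a secondary hypothesis, and another treats it as a measure whose usefulness is still being assessed. Section 3.3.3 records admission and 6-hour values and adds "The difference between CPOi within individuals at admission to ICU and 6h post-operation will be calculated", so there are three candidate contrasts and Hypothesis 2 does not choose among them.

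**Working it through.** **Inputs from the protocol.** 50 patients (trial summary), 1:1 allocation (section 4), hence 25 per arm if all 50 are randomised. PGD 36% versus 22%, two-sided 5%, 400 patients, power 0.85 (sections 2 and 10.2). 5% significance and 80% power for a 30-point PGD reduction (section 7.10). A 30-day survival bound of 88.8% (section 7.10).

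**Step 1. Reproduce the 400.** The two-proportion formula with continuity correction gives 202 per arm, or 404 in total. Exact Fisher power at 200 per arm is 0.851. The uncorrected formula gives 188 per arm (376) and power 0.87 at 200 per arm. The stated figure therefore matches a Fisher or continuity-corrected test.

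**Step 2. Power for the same PGD effect here.** Normal approximation: power = Φ{[δ − 1.96·√(2p̄(1−p̄)/n)] / √[(p₁(1−p₁)+p₂(1−p₂))/n]}, with p₁ = 0.36, p₂ = 0.22, δ = 0.14, p̄ = 0.29. With n = 25 this is Φ(−0.88) = 0.19. Exact power sums the binomial probabilities of all tables with p ≤ 0.05.

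| Per arm | Fisher | Score | Normal approx. |
|---|---|---|---|
| 25 | 0.12 | 0.20 | 0.19 |
| 17 | 0.07 | 0.14 | 0.14 |

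The second row applies if the 50 are eligible hearts, as the denominator in section 10.1 could mean, and two-thirds are randomised: 50 × 2/3 ≈ 33, about 17 per arm. At 25 per arm a true 36% versus 22% effect gives a non-significant result with probability 1 − 0.20 = 0.80 (score) to 1 − 0.12 = 0.88 (Fisher).

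**Step 3. Precision.** The approximate 95% half-width for the PGD difference at 25 per arm is 1.96·√[(0.36×0.64 + 0.22×0.78)/25] = 0.25, against a target difference of 0.14.

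**Step 4. 30-day mortality, illustration only.** Taking 11.2% (100 − 88.8) and assuming it is halved to 5.6%, power at 25 per arm is 0.02 (Fisher) or about 0.10 (score). The protocol mentions log-rank for this outcome; the binary tests are used here as a stand-in. No CPOi variance is given, so no power is calculated for it.

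**Step 5. How many comparisons are listed.** PGD 1 + echo 6 + 30-day mortality 1 + 6-month survival 1 + complications 9 + lengths of stay 2 = 20. CPOi at admission, at 6 hours and as change adds 3, giving 23.

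**Step 6. Chance of at least one false positive** if each were tested at a nominal two-sided 5%. Under independence it is 1 − 0.95^k. Under equal correlation ρ it is simulated from normal test statistics (200,000 draws).

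| Tests | ρ = 0 | ρ = 0.5 | ρ = 0.75 |
|---|---|---|---|
| 20 | 0.64 | 0.42 | 0.26 |
| 23 | 0.69 | 0.45 | 0.27 |
| 3 (PGD, 30-day mortality, one CPOi contrast) | 0.14 | 0.13 | 0.11 |

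Fisher's test is conservative at 25 per arm. With assumed event rates of 2% to 50% and independence, Fisher for the binary outcomes gives about 0.43 for 20 tests and 0.52 for 23. For the three named tests it gives about 0.08.

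**The case against.** The protocol never calls these comparisons confirmatory. It presents a feasibility study, discloses in section 2 that a meaningful difference needs a large sample, and bases its success criteria in 3.3.1 on the feasibility proportion alone. Section 4 explains that the design deliberately replicates the larger trial apart from the primary outcome. Section 10.3.3 is a menu by data type with examples and optional models; no sentence says all 20 components will be tested. It already promises a 95% interval for differences in proportions. Rules on multiplicity and on which analysis leads may sit in a statistical analysis plan that is not shown.

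Most of this stands, and it limits the point. A reader might infer that the plan runs some 20 confirmatory tests at a full 5% with no exploratory label anywhere, so that a chance finding is more likely than not. The documents do not support that. The 5% level is inferred from the 95% intervals and from the early-cessation text in 7.10. CPOi does carry an exploratory label in three places. Hypotheses 1 and 2 themselves cover about three to five tests. A familywise rate above one half needs near-independence or score tests throughout. The absence of an alpha hierarchy is not a finding here, and neither is the lack of a named lead between adjusted and unadjusted results.

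The objection does not remove the wording of 3.2. The limitation is disclosed, yet the hypotheses are still stated as predictions with tests attached. Section 7.10 also speaks of confirming a PGD reduction at 5% within this study, so an inferential reading of PGD is not far-fetched. The CPOi conflict lies inside the protocol.

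**Conclusion.** The point holds as a mismatch between a stated aim and the protocol's own figures. Section 3.2 sets between-arm hypotheses that this study has about 0.12 to 0.20 power to test for PGD at 25 per arm, or 0.07 to 0.14 at about 17 per arm. The clinical endpoints in items v to xi carry no label that would stop those results being read as tests of efficacy. The PGD figures rest only on the protocol's rates, the arm sizes and an inferred two-sided 5% level.

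Multiplicity is secondary. The false-positive chance is roughly 0.26 to 0.69 if all listed comparisons were tested at nominal 5%, and about 0.11 to 0.14 for three tests of the named hypotheses (lower with Fisher). These figures depend on assumed correlations, and the Fisher-based ones also on assumed event rates. They show that an isolated significant result would be weak evidence, not that one is to be expected.

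CPOi's status is a plain internal contradiction. None of this affects the primary feasibility outcome. The change should be made, because it governs what the trial may conclude about the two solutions.

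**What to change.** - **Section 3.2:** replace Hypotheses 1 and 2 with estimation aims, namely to estimate the between-arm difference in PGD, 30-day mortality and CPOi with 95% confidence intervals, to inform the main trial.
- **Section 10.3.3:** state that all between-arm clinical comparisons (items v to xi and CPOi) are exploratory and are reported as estimates with 95% intervals, without significance claims.
- **CPOi:** label it exploratory in the trial summary and in 3.2, to match 3.3.3, 3.3.4 and 7.7, and name one lead contrast. The regression of change adjusted for the admission value, already described in 10.5, would serve.

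The cost is wording at the next amendment, with no extra patients or data. The trial gives up formal significance statements on clinical outcomes, which 50 patients cannot support.
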